6.1 DETERMINATION OF SAMPLE SIZE

The purpose of this trial is hypothesis generation regarding the efficacy of pirfenidone vs. placebo on lung function parameters on the basis of rate of decline in FVC, as measured by daily handheld spirometry.

A total sample size of approximately 250 patients is planned, and patients will be randomized in a 1:1 ratio. The randomization will be stratified by concomitant MMF treatment (yes/no), the presence/absence of IPAF as defined by the MDT.

The planned sample size is based on the statistical hypothesis of the primary endpoint and assumes 80% power and a two-sided significance level of 5% using a student's t-test. It is assumed, after inspection of historical data, that FVC decline in the placebo arm is 85 mL with a common standard deviation of 70 mL, which can be reduced to 60 mL with a common standard deviation of 70 mL in the pirfenidone arm. In this scenario, 125 patients per treatment arm are needed to detect this treatment effect with 80% power.

These assumptions are based upon the following considerations: in IPF, the annual rate of decline of FVC is approximately 200 mL. Owing to the fact that patients with unclassifiable ILD have rates of disease progression in the range of patients with IPF,

albeit with a lower mortality rate (Ryerson et al. 2013), a similar decline rate of 200 mL/year, equivalent to a 100 mL decline over a treatment period of 24 weeks, can be expected. However, a yet unknown proportion of patients in this trial will be treated concomitantly with MMF. In a previous study of CTD-ILD (Fischer et al. 2013), MMF was found to have beneficial effects on lung functions in these patients. While CTD-ILD is a distinct entity from the current trial population, both conditions may share some autoimmune features. Therefore assuming a smaller FVC decline of 85 mL in the placebo arm compared with 60 mL in the pirfenidone arm over the 24-week double-blind treatment period appears justified. In addition, the potential confounding effect of concomitant MMF therapy in these patients justifies stratification to ensure equal distribution of patients who receive and do not receive treatment with MMF.

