4.5 EFFICACY ANALYSIS

The primary and secondary efficacy analyses will include all patients in ITT population, with patients grouped according to their assigned treatment.

Pirfenidone — F. Hoffmann-La Roche Ltd

The primary analysis of the primary efficacy endpoint of this study is planned to be performed when the last patient reached the date of the last follow-up visit after end of the double-blind treatment period (clinical cut-off date).

4.5.1 Primary Efficacy Endpoints

The primary efficacy objective for this trial is to evaluate the efficacy of pirfenidone vs. placebo on lung function parameters on the basis of rate of decline in FVC in mL measured by handheld spirometer over the 24-week double-blind treatment period.

The primary analysis will be based on the ITT population. Patients who discontinue treatment prematurely will be analyzed based on the available data. No imputation method will be applied for the primary endpoint.

The primary analysis of the primary endpoint will compare the mean FVC decline in each treatment arm using a student's t-test with a two-sided significance level α =0.05. The mean FVC decline for each treatment arm will be calculated using the estimated FVC decline for each individual patient. The estimated FVC decline for individual patients will be obtained by applying a linear regression model to all data points collected during the 24-week double-blind treatment period:

$$X_{it} = \alpha_i + \beta_i D_{it} + u_{it}$$

where

 X_{it} = the FVC measurements (mL) of patient i on day t, with i=1,...,N and t=1,...,T, being N the total number of patients randomized and T the total number of days with assessment.

 D_{i*} = study day t of patient i

 α_i, β_i = intercept and slope of the individual linear regression of patient i

The time-adjusted decline for patient i is then obtained by estimating the patients' individual difference in predicted values between baseline and week 24 from the linear regression.

In a further step, the time-adjusted mean FVC decline is estimated by calculating the mean over all individual time-adjusted declines of all patients by treatment arm.

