4.5.8.2 Fixed missing imputation between Q1 and Q3 of Placebo distribution

In another approach to evaluate the robustness of the analysis of the second endpoint to the missing at random (MAR) assumption a tipping point sensitivity analysis will be performed, where missing data of both treatment groups will be imputed by values derived from the range between lower and upper quartile (Q1 - Q3) in the Placebo group at each visit. The aim of the tipping point approach is to assess how severe departures from MAR could be in order to reverse conclusions from the analysis of secondary endpoint under different assumptions for the decline after withdrawal of the randomized treatment.

100 datasets with imputed values will be created for each treatment group. For the first dataset missing values in the respective treatment group will be imputed by the lower quartile (Q1) of placebo group within each visit. In the second dataset, the missing values will be imputed by Q1 plus the amount of $0.01 \times (Q3 - Q1)$. The value added to Q1 will be increased within each subsequent dataset by another amount of $0.01 \times (Q3 - Q1)$, so that in the last of the 100 dataset the amount of Q3 from the placebo group will be imputed for missing values.

Pirfenidone — F. Hoffmann-La Roche Ltd

Then, for each of the 10000 combinations of datasets the decline in FVC (mL) at week 24 will be estimated from a random slope model This model will include fixed effects for the stratifying variables concomitant use of MMF and presence/absence of IPAF and treatment-by time-interaction. Random effects will be included for both time and intercept.

The difference between treatment groups will be calculated together with the respective p-value.

A heat map displaying positive and negative outcome based on the p-values for the comparison pirfenidone versus placebo with green and red colors (green: < 0.05, red: > 0.05) will be provided to illustrate the outcome of this analysis graphically. The robustness of the results will be discussed based on the magnitude of deviations from MAR required to change the results.

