4.5.8.3 Tipping point analysis with shifts

An additional approach is to evaluate the robustness of the analysis of the secondary endpoint to the missing at random (MAR) assumption by performing a tipping point sensitivity analysis using the Multiple Delta Adjustment Method.

As a first step non-monotone missing data will be imputed 100 times using MCMC (Markov Chain Monte Carlo) to generate 100 data sets of longitudinal spirometry data (FVC [mL]) with monotone missingness pattern (PROC MI). Such a missingness pattern is the pre-requisite for subsequently applying sequential imputation and means that once a patient has a missing FVC value at a particular time point, FVC values at all subsequent time points also have missing values. The seed in PROC MI number will be set to 1234.

Once the monotone missing pattern has been created, the tipping point analysis for the longitudinal FVC data will be based on the Multiple Delta Adjustment Method. Data in each of the 100 generated datasets with the monotone missingness pattern will be imputed once by using sequential regression. A delta adjustment will be added to each imputed value. The value of each delta adjustment will be given by shift parameters S_1 and S_2 for the 2 treatments.

For patients with more than one monotone missing visit, multiple adjustments must be applied and since the imputation method is sequential, the effect of the adjustments is cumulative. S1 and S2 therefore represent the slope of a linear adjustment over time. This step will be repeated for a variety of combinations of S1 and S2.

For each combination of shift values S1 and S2 the 100 complete data sets will be analyzed using the statistical model as described above. The estimate of treatment difference at week 24 will be derived. Rubin's rules (16) will be used to combine the results from the analyses for each pair of S1 and S2 (PROC MIIANALYZE). Point estimates for the comparison pirfenidone versus placebo and respective p-values will be reported for selected combinations of S1 and S2 in a cross-table.

The following combinations of S1 and S2 will be applied:

Pirfenidone — F. Hoffmann-La Roche Ltd

- S1 (Pirfenidone): -130, -125,-120,-115,-110,-105,-100,-95,-90,-85,-80,-75,-70,-65,-60,-55,-50,-45,-40,-35,-30,-25,-20,-15,-10,-5,0, 5, 10
- S2 (Placebo): -40,-35,-30,-25,-20,-15,-10,-5,0, 5, 10, 15, 20, 25, 30, 35, 40, 45, 50, 55, 60, 65, 70, 75, 80, 85, 90, 95, 100, 105, 110, 115, 120.

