A heat map displaying positive and negative outcome based on the p-values for the comparison pirfenidone versus placebo with green and red colors (green: < 0.05, red: > 0.05) will be provided to illustrate the outcome of this analysis graphically. The robustness of the results will be discussed based on the magnitude of deviations from MAR required to change the results (Rubin, 1987). Pharmacokinetic and Pharmacodynamic Analyses

No pharmacokinetic or pharmacodynamic analyses are planned for this study.

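### The tipping-point heat maps in SAP 4.5.8.2 and 4.5.8.3 are coloured by p-value alone, so a scenario in which placebo is significantly better would be labelled a positive outcome

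*SAP*

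**What the plan says.** SAP 4.5.8 tests how robust the secondary FVC analysis is to the MAR assumption. I take this endpoint to be site-measured FVC in mL, which SAP 4.5.6 calls the key secondary endpoint. Two of the three approaches end in a heat map.

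- **4.5.8.2** fills missing values in each arm with values stepped between the placebo lower and upper quartiles, giving 100 x 100 combinations. Its aim is to learn "how severe departures from MAR could be in order to reverse conclusions from the analysis of secondary endpoint". The display is "A heat map displaying positive and negative outcome based on the p-values", "with green and red colors (green: < 0.05, red: > 0.05". The difference and p-value are calculated for every combination, but no table of them is specified.
- **4.5.8.3** adds a shift S1 (pirfenidone) or S2 (placebo) to each imputed value, cumulative over missing visits. It introduces the grid with "The following combinations of S1 and S2 will be applied": S1 runs from -130 to +10 mL and S2 from -40 to +120 mL, in steps of 5. The display is "A heat map displaying positive and negative outcome based on the p-values for the comparison pirfenidone versus placebo with green and red colors", and the colour rule is the same as in 4.5.8.2. Estimates and p-values are also tabulated, but only for a selection of S1/S2 pairs.

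Section 4.5.8 does not say whether its p-values are one- or two-sided. SAP 4.5.1 specifies for the primary endpoint a "student's t-test with a two-sided significance level" of 0.05.

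**The concern.** A two-sided p-value carries no sign. Most of the S1/S2 grid makes pirfenidone worse and placebo better, which is right for a tipping-point analysis. If the missing fraction is large enough, the estimate passes through zero along that path and then becomes significant in favour of placebo. Under the stated rule that region turns green again, the colour assigned to a positive outcome, although it is the complete reversal that the analysis sets out to find. A reader who takes the legend at its word, or who sums the green area, would credit adverse scenarios to pirfenidone.

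**Working it through.** **Inputs from the documents.** Protocol 6.1 "assumes 80% power and a two-sided significance level of 5% using a student's t-test" and takes it that "FVC decline in the placebo arm is 85 mL with a common standard deviation of 70 mL", against 60 mL on pirfenidone, with 125 patients per arm. The S1 and S2 values are those listed in SAP 4.5.8.3.

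**Assumptions.** The SD of 70 mL and the 25 mL effect were set for home spirometry and are borrowed here for site FVC. The effects of 50, 90 and 100 mL are illustrative. The missing fraction m is not given; SAP 4.5.8 says only that the number is known. A patient with missing data is taken to miss k final visits, with k uniform on 1 to 6.

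**1. The plan's own figure.** n per arm = 2 x (1.96 + 0.8416)^2 x (70/25)^2 = 2 x 7.849 x 7.84 = 123.1, so 124. Exact t-test power at 125 per arm is 80.3%. The stated 125 is reproduced. This only checks the inputs.

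**2. Sign-blindness of the rule.** SE = 70 x sqrt(2/125) = 8.85 mL and t = 25/8.85 = 2.82 on 248 df, so two-sided p = 0.0051. A difference of -25 mL gives the same p. Both cells would be green.

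**3. Approximation over the grid.** There are 29 S1 values and 33 S2 values, so 957 cells. Positive differences favour pirfenidone.

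- Difference = effect + m x E[k] x (S1 - S2), with E[k] = 3.5.
- Variance of the difference = {2 x 70^2 + (m x E[k^2] - m^2 x E[k]^2) x (S1^2 + S2^2)} / 125, with E[k^2] = 91/6 = 15.17.

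Worked cell: S1 = -130, S2 = +120, effect 25 mL, m = 10%. The difference is 25 - 0.10 x 3.5 x 250 = -62.5 mL. The variance is {9,800 + 1.394 x 31,300}/125 = 427.5, so SE = 20.7, t = -3.02 and p = 0.003. The cell favours placebo and would be green. In the same corner, m = 5% gives -18.8 mL (p = 0.25, red), 7.5% gives -40.6 mL (p = 0.030) and 20% gives -150 mL (p < 0.0001).

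Cells that would be green while favouring placebo, out of 957:

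| Effect | m = 5% | 10% | 15% | 20% |
|---|---|---|---|---|
| 25 mL | 0 | 191 (20%) | 464 (48%) | 616 (64%) |
| 50 mL | 0 | 0 | 178 (19%) | 374 (39%) |
| 90 mL | 0 | 0 | 0 | 89 (9%) |
| 100 mL | 0 | 0 | 0 | 45 (5%) |

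At 25 mL the first such cells appear between 5% and 7.5% missing (20 cells at 7.5%). If patients miss at most three final visits (k uniform on 1 to 3), the 25 mL row becomes 0, 0, 165 (17%) and 360 (38%).

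**4. Cross-check.** A simulation with sequential imputation, cumulative shifts, per-patient slopes and Rubin's rules (30 trials per scenario, 20 imputations) gave 14%, 42% and 59% of cells at 10%, 15% and 20% dropout for 25 mL. For 90 mL it gave 0%, 0.6% and 6%. The pattern agrees with the table.

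**5. The 4.5.8.2 map.** The least favourable corner (pirfenidone at the placebo lower quartile, placebo at its upper quartile) was simulated with per-patient slopes, a 25 mL effect and an assumed baseline FVC SD of 600 to 800 mL. It was green while favouring placebo in about 7 to 11% of simulated trials at 5% missing, 45 to 56% at 10% and 94% at 20%.

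**6. Does the tipping boundary move?** Without shift inflation, differences within 1.97 x 8.85 = 17.4 mL of zero are red, a band 34.9 mL wide. One 5 mL grid step moves the difference by 5 x 0.20 x 3.5 = 3.5 mL at 20% missing, and by 5.25 mL at 30%. The band is therefore about 10 or 7 steps wide, and wider once the shift variance is added. The two green regions cannot touch.

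**The case against.** The strongest reply is that the SAP judges robustness by how far from MAR one must go to change the result, not by counting green cells. That distance runs from S1 = S2 = 0 to the first loss of significance, and step 6 shows that a sign condition leaves it unchanged. This stands. A reader might infer that the maps overstate robustness. The documents do not support that, except for someone who reads green area as evidence or takes the far region at its label.

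The numerical inputs are also open to challenge. The 25 mL effect and 70 mL SD belong to the home-spirometry endpoint, the larger effects are not in the documents, and the missing fraction is not stated. The calculations use simple slope comparisons, whereas 4.5.8.2 fits a random-slope model and 4.5.8.3 uses 100 imputations. This stands too: the table shows when such cells could arise, not that they do.

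It is tempting to say that every test in the SAP is two-sided. Only the primary t-test is described so; for 4.5.8 it is an inference. A one-sided p-value in the direction of benefit would remove the problem.

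Finally, the 4.5.8.3 table shows direction for the S1/S2 pairs selected, and a careful reader could recognise the far green region by its position. This helps in part. In 4.5.8.2 nothing is specified beyond the map.

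**Conclusion.** The concern holds as a fault in the display rule. As written, both maps would label a scenario with placebo significantly better as positive, which contradicts the stated purpose of finding what reverses the conclusion. This rests on two-sided p-values in 4.5.8, inferred from 4.5.1.

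The extent cannot be fixed from the documents. Under the stated assumptions it ranges from no cells at 5% missing to about 64% of the S1/S2 grid at 20% missing for a 25 mL effect, and it is nil up to 15% and roughly 5 to 9% at 20% for a 90 to 100 mL effect.

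The grade is minor. These are sensitivity analyses of a secondary endpoint whose p-values SAP 4.5.3 calls descriptive, in a trial that SAP 2.3 describes as hypothesis-generating. A reader might infer that the primary test, its alpha or the tipping boundary is affected; none of them is.

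**What to change.** In both 4.5.8.2 and 4.5.8.3, state that p-values are two-sided and replace the colour rule with three classes:

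- green if the estimate favours pirfenidone and p<0.05;
- red if p>=0.05, which also covers p exactly 0.05, now unassigned;
- a third colour if the estimate favours placebo and p<0.05.

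A zero-difference contour on each map would help but is optional. The cost is about two sentences of SAP text and a small change to the plotting code. No data, imputation or model changes. The sponsor already holds the missing counts, so it can see at once whether any cell changes colour.

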4.6 SAFETY ANALYSES

All safety analyses of data from the double-blind treatment period will be based on the safety population, i.e., the safety population will include all randomized patients who received at least one dose of trial treatment, with patients grouped according to treatment received. Safety data from the follow-up period will be summarized based on the safety follow-up population.

The safety objective for this trial is to evaluate the safety of pirfenidone vs. placebo.

No formal statistical testing will be performed for safety parameters.

Data collected during the 12-month safety follow-up will be analyzed separately (see section 4.7).

The safety analysis will involve investigating the nature, frequency, severity, and timing of treatment-emergent adverse events. The specific parameters that will be investigated include all adverse events, adverse events Grade ≥3 according to the NCI CTCAE version 4.03, adverse events of special interest, and serious adverse events. The primary interest in this trial will be adverse events Grade ≥3 related to pirfenidone or placebo.

Prior to the first administration, only serious adverse events caused by a protocol-mandated intervention will be recorded. These adverse events will be listed.

The incidence, type, and severity of adverse events will be summarized according to the primary System Organ Class (SOC) and within each SOC, by the Medical Dictionary for Regulatory Activities (MedDRA) version 20.1 or higher preferred term.

Adverse events Grade ≥3, adverse events of special interest, and serious adverse events will be analyzed in a similar way to all adverse events.

Pirfenidone — F. Hoffmann-La Roche Ltd

Descriptive statistics will be presented for dose modifications and treatment interruptions. Adverse events leading to treatment interruption or dose modification will also be summarized.

Laboratory parameters including hematology and the chemistry panel will be presented in shift tables of NCI-CTCAE version 4.03 grade at baseline vs. worst grade during treatment period. The laboratory parameters will be presented according to means, standard deviation, minimum, and maximum. Selected laboratory parameters will be also graphically presented over time. Liver abnormalities for the parameters total bilirubin, alkaline phosphatase, ALAT (SGPT) and ASAT (SGOT)) will be also presented.

The results from the 12-lead ECGs will be summarized and presented.

4.6.1 Exposure of Study Medication

All analyses described in this section refer to the data collected in the drug-log for the double-blind randomized treatment period. Unknown doses will be excluded from the exposure analyses.

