4.6.1.1 Treatment duration

Summaries of dosing, treatment duration, dose interruptions or reductions during the randomized double-blind treatment period will be provided for each treatment arm separately.

The overall treatment duration (weeks), including and excluding dose interruptions, will be summarized descriptively by treatment arm. The overall treatment duration including dose interruptions will be defined as follows:

[Date of last positive dose of randomized treatment received (pirfenidone/placebo) – date of first intake of randomized treatment) + 1)] / 7.

The overall treatment duration excluding dose interruptions will be derived from the treatment administration panels using the time windows described above, considering only days on treatment. i.e. positive dose.

Details on treatment administration, reductions or interruptions will be listed.

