4.6.1.2 Doses and Dose modifications or interruptions

The total dose (mg), the average daily dose (mg/d) and the last dose administered (mg/d) will be presented descriptively for each of the study treatments.

The average daily dose will be calculated by summing up the number of capsules taken, divided by the overall treatment duration including dose interruptions as defined above.

Numbers and proportions of patients with at least one dose modification, or drug interruption, will be presented for each treatment arm separately. Numbers and proportions of patients with 1, 2, 3 or more dose modifications, or treatment interruptions, will be given.

Pirfenidone — F. Hoffmann-La Roche Ltd

The total number of dose modifications, reductions or treatment interruptions, will be presented together with numbers and frequencies of reasons for dose modification, reduction or treatment interruption.

Dose modifications, reductions or treatment interruptions will be presented as given in the drug logs dose strength and number of capsules taken.

In addition, dose intensity will be analyzed descriptively by treatment arm over time. For calculation of dose intensities, the time from first administration of randomized treatment to the end date of randomized treatment will be considered. The following formula will be used for calculation:

Dose intensity (DI) = (total dose received / total dose planned)*100.

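### Unknown doses add no capsules to average daily dose, but their days stay in its denominator and are scored as zero dose

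*SAP*

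**What the plan says.** Four statements in SAP 4.6.1 to 4.6.1.2 bear on this.

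- **Unknown doses (4.6.1).** "Unknown doses will be excluded from the exposure analyses". Nothing is said about the days to which those doses belong.
- **Duration (4.6.1.1).** Duration including interruptions is a date difference, "Date of last positive dose of randomized treatment received (pirfenidone/placebo) – date of first intake of randomized treatment", plus 1, divided by 7. A second duration, which excludes interruptions, is built by "considering only days on treatment. i.e. positive dose".
- **Average daily dose (4.6.1.2).** It is obtained by "summing up the number of capsules taken, divided by the overall treatment duration including dose interruptions", so the first of the two durations is the denominator.
- **Dose intensity (4.6.1.2).** "Dose intensity (DI) = (total dose received / total dose planned)*100". Its period is given separately: "the time from first administration of randomized treatment to the end date of randomized treatment will be considered". The planned total is not defined further.

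SAP version 2.0 has the same rule and formulas in its sections 4.7.1 to 4.7.1.2. SAP 4.7 applies the approach to exposure in the open-label safety follow-up, for treatment duration and amount of drug taken.

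**The concern.** The average daily dose denominator is built from two dates, not from drug-log records. Deleting a record in the middle of treatment removes its capsules and leaves the denominator unchanged. Excluding an unknown dose under these formulas therefore gives the same result as recording a zero. The duration that excludes interruptions behaves similarly: an unknown day is not a recorded positive-dose day, so it drops out as an interruption would.

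What is at stake is how the exposure tables are read. Average daily dose and dose intensity show how close patients stayed to the protocol dose, and both are presented by arm. A patient with an incomplete log but full intake would appear to have had less drug.

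**Working it through.** **Inputs from the documents**

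- Capsule strength 267 mg; full dose nine capsules a day (protocol 4.3.2.1). Check: 9 × 267 = 2403 mg/d, the stated daily dose.
- Titration (protocol Table 2): three capsules a day on days 1–7, six on days 8–14, nine from day 15.
- Double-blind treatment 24 weeks = 168 days (protocol 3.3.1).

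**Assumptions**

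- The numbers of unknown-dose days (7, 14, 28) are illustrative.
- Results are converted to mg and days. Taken literally, the formula gives capsules per week (1449 / 24 = 60.4) although the SAP labels the result mg/d. That is a separate point.

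**Reference patient, full intake**

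- Capsules: 7 × 3 + 7 × 6 + 154 × 9 = 1449
- Dose: 1449 × 267 = 386,883 mg
- Average daily dose: 386,883 / 168 = 2302.9 mg/d

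**Rule as written, u unknown days in mid-treatment, drug actually taken**

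Average daily dose = (386,883 − u × 2403) / 168

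| u | mg left in numerator | Average daily dose (mg/d) | Error |
|---|---|---|---|
| 7 | 370,062 | 2202.8 | −4.3% |
| 14 | 353,241 | 2102.6 | −8.7% |
| 28 | 319,599 | 1902.4 | −17.4% |

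**Cases where the rule does little or no harm**

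- *14 mid-treatment unknown days, no drug taken.* The rule gives 353,241 / 168 = 2102.6 mg/d, which is the true value.
- *Last 14 days unknown, drug taken.* The last known positive dose is now day 154, so the span shortens: 353,241 / 154 = 2293.8 mg/d, −0.4%.

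**Dose intensity**

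If the planned dose is taken over all 168 days, the mid-treatment cases give 370,062 / 386,883 = 95.7%, 353,241 / 386,883 = 91.3% and 319,599 / 386,883 = 82.6%, against a true 100%. If unknown days are left out of the planned dose, all three give 100%. The SAP does not say which applies.

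**Removing unknown days from both sides**

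- Drug taken, mid-treatment: 370,062 / 161 = 2298.5 (−0.2%); 353,241 / 154 = 2293.8 (−0.4%); 319,599 / 140 = 2282.8 (−0.9%). Dose intensity is 100% each time.
- 14 mid-treatment days unknown and not taken: 353,241 / 154 = 2293.8 against a true 2102.6, +9.1%. Dose intensity is 100% against a true 91.3%.
- Titration days 2–7 unknown, drug taken: (386,883 − 6 × 801) / 162 = 2358.5, +2.4%. The rule as written gives 382,077 / 168 = 2274.3, −1.2%.

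**The case against.** The strongest reply is that the exclusion applies to the exposure analyses as a whole, and those include duration. The whole record, dose and days, might be meant to go. That intention is possible, but the average daily dose formula does not carry it out: an interior record can be deleted without changing either date. If this is what the sponsor means, it needs to be written.

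Three further points stand and limit the finding.

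- A reader might infer that exposure is understated for every patient with gaps in the log. The two counter-cases above show otherwise. Interruptions recorded as zero are not unknown doses, and they belong in this denominator by design.
- A reader might also infer that dose intensity is certainly understated, for example 83% for 28 days. That figure assumes a planned dose covering the whole window. Dose intensity has its own period, running to the end date of treatment rather than to the last positive dose, and its planned total is undefined.
- A reader might infer that missing entries would inflate the counts of dose reductions or interruptions, or would create a false tolerability difference between arms. The documents do not support this. Modifications, reductions and interruptions are tabulated with reasons from the drug log (SAP 4.6.1.2), not derived from average daily dose. Nothing suggests that record-keeping differs by arm in this double-blind trial.

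It is also fair to object that removing unknown days from both sides swaps one assumption for another: dosing on unknown days is taken to resemble dosing on known days. The +9.1% case shows the cost when that is wrong.

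**Conclusion.** For average daily dose the inconsistency follows from the text: an unknown dose before the last known positive dose is scored as zero rather than excluded. The understatement is 4.3%, 8.7% and 17.4% for 7, 14 and 28 such days in a fully adherent 168-day patient, given that the days are mid-treatment at full dose and the drug was taken. Its actual size in this trial cannot be stated, because the frequency of unknown doses is not given. For dose intensity the finding is an ambiguity to settle, not an established error.

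The point is minor. The outputs are descriptive, SAP 4.6 plans no formal testing of safety parameters, and no efficacy analysis uses these quantities.

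**What to change.** Add to SAP 4.6.1 that days with an unknown dose are removed from both the numerator and the denominator of average daily dose, and from the planned dose in dose intensity. Define the planned dose at the same time. Report, per arm, the number of unknown-dose days and the number of patients with any. Show the same summaries with unknown days counted as zero, as the lower bound.

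The counts and the second set of figures are needed because removing the days overstates exposure when the drug was not taken. If the counts are small, the choice will not matter and the table will show that.

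The cost is one or two sentences, a small programming change and a few extra table rows. The rule was already in SAP version 2.0, and SAP 4.5.8 dates the primary analysis to March 2019. For the double-blind period the change should therefore be labelled as made after that analysis, and keeping the zero-dose version beside it preserves comparability. The same sentence should cover the open-label exposure tables in SAP 4.7.
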